6.2.3. Quantitative Performance Targets

The following quantitative performance targets have been set in order to conclude that the new simultaneous dual-tracer techniques provide images of each tracer that are equivalent to images that would be obtained from separate, single-tracer scans of each tracer:

- (1) dual-vs.-single correlation coefficients ≥ 0.95 for both image voxels and lesion SUVs;

- (2) bias, as measured by the linear regression slope, to be within 5% of 1.0 ($0.95 \leq \text{slope} \leq 1.05$);
- (3) bias, as measured by the linear regression intercept, to be within 5% (of mean voxel or SUV value) of zero; and
- (4) tumor and background tissue SUVs for dual-tracer images within 0.05 of those for the separate-scan standard images (to 95% power).

These analyses will be repeated for all 3 tracer pairs.

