6.3. Justification of Sample Size

The following sample size calculations are based on testing the hypothesis that differences in SUV_{mean} for lesions and normal tissue regions in images recovered from dual-tracer scanning for each tracer are less than 5% different than those from the single-tracer “standard” images, using a 2 sided *t*-test with alpha = 0.05 and desired power = 0.95. We also assume a standard deviation of 10% for SUV_{mean} measurements (based on PET test-retest variability). This gives a required sample size of $N = 104$. Assuming 5-7 regions/lesions per subject, this gives 15-20 subjects needed to obtain the desired statistical power, which supports our design of 15-20 patients each for each study Arm.

The study design and data analysis techniques were reviewed and approved by the NIH study section for grant 2R44CA257522, and no issues or concerns were noted.

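### Target (4) cannot be applied as an equivalence rule as written: its scale, summary and pass rule are not stated, and the only test named does not test equivalence

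*Combined protocol and SAP*

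**What the plan says.** Section 6.2.3 lists four targets that "have been set in order to conclude that the new simultaneous dual-tracer techniques provide images of each tracer that are equivalent" to those from separate single-tracer scans. Target (1) is a limit on correlation. Targets (2) and (3) each say what the 5% refers to: "bias, as measured by the linear regression slope, to be within 5% of 1.0" and "bias, as measured by the linear regression intercept, to be within 5% (of mean voxel or SUV value) of zero". Target (4) reads "tumor and background tissue SUVs for dual-tracer images within 0.05 of those for the separate-scan standard images (to 95% power"). It gives no unit, no summary (each region or a mean) and no choice between SUVmean and SUVmax, both of which section 5.2 records.

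Section 6.3 sizes the study on the hypothesis that SUVmean differences "are less than 5% different than those from the single-tracer" standard, "using a 2 sided *t*-test with alpha = 0.05 and desired power = 0.95". It takes an SD of 10% for SUVmean "measurements (based on PET test-retest variability"), obtains N = 104, and continues: "Assuming 5-7 regions/lesions per subject, this gives 15-20 subjects needed to obtain the desired statistical power".

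Section 6.2.2 gives regression slope, intercept and Pearson correlation as the measures. No equivalence test, confidence-interval rule or limits of agreement appears in the document.

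**The concern.** An equivalence claim needs a margin on a stated scale, a summary to compare with it, and a rule that controls the chance of a wrong claim. Target (4) supplies only the digits of a margin. Whoever analyses the data must choose the unit, the summary and the rule, possibly after seeing the results.

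The one test named does not fill the gap. A two-sided t-test asks whether the mean difference is zero. A non-significant result does not show that the difference is under 5%, and a significant one does not show that it is over 5%. The plan does not say how the result would be read.

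At stake is the conclusion on whether individual-tracer images can be recovered accurately enough from dual-tracer data. The other targets cannot fully cover for target (4). Because all four are listed together, targets (1) to (3) can block a false claim of equivalence but cannot rescue a technique that target (4) wrongly fails.

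**Working it through.** **1. The plan's own figure.** From 6.3: margin 5%, SD 10%, two-sided alpha 0.05, power 0.95. Two independent means, normal approximation: n = 2 × (1.960 + 1.645)² × (10/5)² = 103.96, so 104. It reproduces.

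The formula depends only on the ratio of SD to margin, so 104 does not by itself establish a relative 5%. Two one-sided tests (TOST) at alpha 0.05 each, with zero true bias, use 1.645 for alpha and 1.960 for power, and so give the same 103.96.

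**2. Scale.** An absolute 0.05 equals 5% only at SUV 1. At an assumed SUV of 5 it is 0.05/5 = 1%, and at 10 it is 0.5%. With an SD of 10% of SUV, the 6.3 formula at SUV 5 gives 2 × (3.605)² × (0.5/0.05)², about 2,600 regions. The wording of 6.3 and of targets (2) and (3) points to a relative 5%.

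**3. Mean or each region.** With zero bias, the share of regions within ±5% is 2Φ(5/SD) − 1. That is 68%, 38% and 28% at paired SDs of 5%, 10% and 14.1%.

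**4. The t-test used as a pass rule, independent regions.** Assumption: non-significance counts as a pass. The plan gives no SD for the paired difference. The 6.3 formula implies 10% × √2 = 14.1%; 5% and 10% are assumed. Values below 14.1% are plausible, since recovered and true values come from the same scan and section 6.1 notes that test-retest differences can exceed recovery errors. The 15-subject arms at 5 regions each give 75 regions; 104 is the plan's N. Paired t-test by noncentral t, df = n − 1, noncentrality = bias/(SD/√n):

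| Paired SD | True 2% bias fails, 75 / 104 | True 5% bias passes, 75 / 104 | TOST passes a 2% bias, 75 / 104 |
|---|---|---|---|
| 5% | 93% / 98% | under 0.001% | over 99.9% |
| 10% | 40% / 52% | 1.0% / 0.1% | 82% / 92% |
| 14.1% | 23% / 30% | 14% / 5% | 56.5% / 69% |

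TOST at ±5% passes a true 5% bias 5% of the time at each SD.

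**5. The same rule with clustering.** Take 15 subjects × 5 regions, paired SD 10%, tested on subject means (df = 14). The SD of a subject mean is 10 × √((1 + 4ρ)/5), with the within-subject correlation ρ assumed:

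| ρ | SD of subject mean | True 5% bias passes | True 2% bias fails | TOST power, zero bias | TOST power, 2% bias |
|---|---|---|---|---|---|
| 0.1 | 5.29% | 7.5% | 27.6% | 0.93 | 0.67 |
| 0.3 | 6.63% | 22.5% | 19.3% | 0.74 | 0.50 |
| 0.5 | 7.75% | 35.7% | 15.4% | 0.54 | 0.37 |

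At paired SD 5% the order reverses. A 2% bias fails 78%, 58% and 46% of the time, and a 5% bias passes less than 0.4% of the time.

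**6. What 104 regions buys under TOST.** With SD 14.1%, zero bias and independent regions, t-based power is 0.947 at 104 regions and 0.835 at 75.

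**The case against.** The t-test appears only in the sample-size section. Target (4) can be read as a plain numeric limit on an observed value, like targets (1) to (3), which also lack confidence intervals. On that reading the error rates above do not arise, and all that is missing is a unit and a summary. This is fair, and it is why those rates are conditional. But a bare limit on the estimate has no error control, and it leaves the reference to 95% power with no function.

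The design is also closer to equivalence than the test named suggests: the 6.3 hypothesis is in equivalence form, and its N agrees with TOST at zero bias. A reader might infer that the sample size was calculated wrongly. The arithmetic does not support that; the gap is in the decision rule.

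A reader might also infer that the main danger is failing a good technique. That holds at a small paired SD or with independent regions. It does not hold at SD 10% with correlation of 0.3 or more, where passing a true 5% bias is the more frequent error. The plan gives neither quantity, so it does not settle the direction.

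Finally, the primary objective (1.1) is to acquire data and the secondary (1.2) is exploratory. That limits the consequence but does not supply the missing rule.

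**Conclusion.** The point holds. Target (4) does not state its scale, its summary or its pass rule, and the test named in 6.3 does not test the hypothesis written there. A relative 5% on the mean of SUVmean is the likely intent, but the text does not settle it.

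If non-significance were taken as a pass, the error rates would depend on the paired SD and on clustering and would not be tied to the margin. Over the assumed range, a 2% bias fails between 15% and 98% of the time, and a 5% bias passes between practically never and 36% of the time. These figures rest on that reading of the t-test, on normal differences, and on assumed values for bias, paired SD and correlation. They concern target (4) alone.

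The documents do not support a claim that the study will in fact use non-significance as its rule, that N = 104 is an error, or that the data acquisition is compromised. The effect is confined to the equivalence conclusion, and the text should be corrected before that conclusion is drawn.

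**What to change.** Replace target (4) with: *for each tracer in each pair, the 90% confidence interval of the mean paired percent difference in SUVmean, (recovered minus true)/true, lies within ±5% (two one-sided tests, alpha 0.05 each), with the interval allowing for several regions per subject.* The mean is proposed because the t-test in 6.3 concerns a mean; if every region is meant, the plan should say so.

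Delete the bracketed reference to power from the target. Name the same test in 6.3, and state there that 104 regions gives about 95% power only with zero true bias, independent regions and a difference SD of about 14%.

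Limits of agreement, separate lesion and background results, and an absolute margin for low-uptake regions are optional additions.

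The cost is wording and a little analysis work, with no change to scans or enrolment. The real price is that the stated power becomes conditional and can fall: with 15 × 5 regions, SD 10% and correlation 0.1 to 0.5, from 0.93 to 0.54 at zero bias and from 0.67 to 0.37 at 2% bias.

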6.3. Justification of Sample Size

The following sample size calculations are based on testing the hypothesis that differences in SUV_{mean} for lesions and normal tissue regions in images recovered from dual-tracer scanning for each tracer are less than 5% different than those from the single-tracer “standard” images, using a 2 sided *t*-test with alpha = 0.05 and desired power = 0.95. We also assume a standard deviation of 10% for SUV_{mean} measurements (based on PET test-retest variability). This gives a required sample size of $N = 104$. Assuming 5-7 regions/lesions per subject, this gives 15-20 subjects needed to obtain the desired statistical power, which supports our design of 15-20 patients each for each study Arm.

The study design and data analysis techniques were reviewed and approved by the NIH study section for grant 2R44CA257522, and no issues or concerns were noted.

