6.2.2. Quantitative Performance Measures

Pixelwise Linear Regression Analysis: The overall accuracy of image pixels for each tracer will be measured by performing linear regression analysis for recovered vs. true image pixel values over all image pixels. This will be computed for each tracer for each patient. The regression slope, intercept, and Pearson’s correlation coefficient will be used as measures of bias between the recovered and true image pixels.

Linear Regression Analysis of ROIs: The accuracy of ROI values for lesions and normal background tissues will also be measured using linear regression analysis of the recovered vs. true values. The regression slope, intercept, and Pearson’s correlation coefficient will be used as measures of bias between the recovered and true ROI values.

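### Section 6.3 counts regions within a patient as independent and gives no credit for pairing, so the stated 0.95 power for each arm is not established

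*Combined protocol and SAP*

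**What the plan says.** Section 6.3 sizes the study to show that recovered SUVmean values are "less than 5% different than those from the single-tracer" standard images. It uses a two-sided t-test at alpha 0.05 with power 0.95 and a "standard deviation of 10% for SUV_{mean} measurements (based on PET test-retest variability". It reports N = 104 and then divides by regions per patient: "Assuming 5-7 regions/lesions per subject, this gives 15-20 subjects needed to obtain the desired statistical power". The same sentence goes on to treat this result as backing for the chosen arm sizes: "which supports our design of 15-20 patients each for each study Arm". It does not say whether the t-test is paired.

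Section 1.0 fixes Arms 1 and 2 at 15 subjects and Arm 3 at 20.

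Section 6.2.3 sets targets for concluding that the recovered images are "equivalent to images that would be obtained from separate, single-tracer scans of each tracer". Target (4) asks for "tumor and background tissue SUVs for dual-tracer images within 0.05 of those for the separate-scan standard images (to 95% power". The section closes with "These analyses will be repeated for all 3 tracer pairs".

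For region values, section 6.2.2 gives only regression: "The accuracy of ROI values for lesions and normal background tissues will also be measured using linear regression analysis". Section 6.1 explains that the true single-tracer components of each synthesized image are known exactly, so the data serve as their own controls. It adds that test-retest differences can exceed the errors in recovered images.

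**The concern.** The calculation departs from the design in two ways that pull in opposite directions. It ignores pairing, and it takes its SD from test-retest variability, which is not the variability of recovered minus true within the same scans. Both probably make it conservative. Against that, it counts each region as an independent observation. Regions of one patient share the same scans, co-registration and signal separation, so their errors may be correlated, and any positive correlation makes the effective sample smaller than the region count.

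Target (4) makes 95% power part of the condition for concluding equivalence, separately for each tracer pair. Each 15-subject arm therefore has to support the figure alone. No clustering method is given for the region-level comparison, and the t-test appears only in 6.3. If equivalence were tested on regions as though they were independent, the interval would be too narrow and equivalence would be declared at the margin more often than the nominal rate.

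**Working it through.** **Inputs from 6.3 and 1.0:** difference 5%, SD 10%, two-sided alpha 0.05, power 0.95, 5-7 regions per subject, arms of 15, 15 and 20. **Not in the documents, so assumed below:** the intraclass correlation (ICC) of recovered-minus-true differences within a patient, and the SD of those differences.

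**1. Reproducing N = 104** (normal approximation)
- Unpaired, per group: 2 × (1.960 + 1.645)² / (5/10)² = 103.96, so 104.
- Paired with zero recovered-true correlation (SD of differences 10% × √2 = 14.14%): also 103.96.
- Unpaired equivalence by two one-sided 5% tests, margin 5%, true difference zero: also 103.96.
- Paired with SD of differences 10%: (1.960 + 1.645)² / 0.5² = 51.98, so 52 (54 with the t correction).

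The stated figure reproduces, but only where pairing earns nothing.

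**2. From regions to patients**
104/7 = 14.9, 104/6 = 17.3 and 104/5 = 20.8 subjects. Conversely, 104/15 = 6.93 and 104/20 = 5.2 regions per subject on average.

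**3. Power on the 6.3 formula, ICC 0** (unpaired t-test)

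| Subjects | 5 regions | 6 regions | 7 regions |
|---|---|---|---|
| 15 | 75: 0.860 | 90: 0.916 | 105: 0.950 |
| 20 | 100: 0.940 | 120: 0.971 | 140: 0.986 |

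At 15 × 7 there is no room for clustering: the largest ICC that keeps 0.95 on this formula is (105/103.96 − 1)/6 ≈ 0.002.

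**4. Paired analysis with the patient as the unit (assumed inputs)**
With m regions per patient, the SD of a patient mean is SD × √((1 + (m − 1) × ICC)/m). Power comes from the noncentral t with k − 1 degrees of freedom for k patients, at a 5% difference. Example: SD 10%, m = 7, ICC 0.3 gives 10 × √(2.8/7) = 6.32%, noncentrality 5 × √15 / 6.32 = 3.06, power 0.812.

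| k | Paired SD | ICC | 5 regions | 6 regions | 7 regions |
|---|---|---|---|---|---|
| 15 | 10% | 0 | 0.980 | 0.993 | 0.997 |
| 15 | 10% | 0.1 | 0.925 | 0.949 | 0.964 |
| 15 | 10% | 0.3 | 0.775 | 0.797 | 0.812 |
| 15 | 7% | 0.3 | 0.972 | 0.978 | 0.982 |
| 20 | 10% | 0.1 | 0.980 | 0.989 | 0.993 |
| 20 | 10% | 0.3 | 0.892 | 0.907 | 0.918 |

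With paired SD 10%, power falls to 0.95 at an ICC of about 0.06-0.12 for 15 patients and 0.18-0.24 for 20. With paired SD 7%, 15 patients keep 0.95 up to an ICC of about 0.39-0.43.

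**5. Error at the margin if equivalence were tested on regions, ignoring clustering**
False-equivalence rate = 1 − Φ(1.645 / √(1 + (m − 1) × ICC)), nominal 5%.
- ICC 0.1: m = 5 gives 1 − Φ(1.645/√1.4) = 0.082; m = 7 gives 1 − Φ(1.645/√1.6) = 0.097.
- ICC 0.3: m = 5 gives 1 − Φ(1.645/√2.2) = 0.134; m = 7 gives 1 − Φ(1.645/√2.8) = 0.163.

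A simulation of 15 × 7 regions with the true difference at the margin gave 0.097 and 0.162 for the region-level test, and 0.050 in both cases for a test on patient means. A smaller SD does not remove this inflation, which depends only on ICC and regions per patient.

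**The case against.** The strongest reply is that the shortfall at 5 or 6 regions belongs to a formula that does not fit the design. The comparison is paired, and with a paired SD of 10% about 52-54 independent regions suffice, fewer than the 75 given by 15 patients with 5 regions each. Since 6.1 says test-retest differences can exceed recovery errors, the true paired SD may be well below 10%. This stands. A reader might infer from the unpaired figures that Arms 1 and 2 are underpowered, and the documents do not support that.

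Nor do they support reading the requirement as 7 regions in every subject. An average of about 6.9 meets N = 104, normal tissue regions count as well as lesions, and no cap is set. Seven may be reachable, but the plan does not fix the number.

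The error rates in step 5 concern an analysis the plan does not specify. A reader might take the 16% figure as the study's error rate; it is the 7-region end of the 13-16% range at an assumed ICC of 0.3.

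Finally, the primary objective is to acquire data for algorithm development, the protocol says this is not an NIH-defined clinical trial, and the grant's study section raised no concern. That limits the weight of the point. It does not supply the missing inputs, and the plan itself sets equivalence targets and a 0.95 power claim. The correlation target of at least 0.95 in 6.2.3 does not fill the gap either: it is a success criterion, not a design value for the SD of differences.

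**Conclusion.** The point holds as a gap in the justification. N = 104 reproduces, but it gives no credit for pairing and treats regions of one patient as independent, so 0.95 power for each arm is not established. Even with zero within-patient correlation, the formula supports 0.95 in the 15-subject arms only at the top of the stated 5-7 range; Arm 3 misses only at 5 regions, and only slightly (0.94).

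Net power cannot be computed from the documents. For 15 patients it exceeds 0.95 under some plausible-looking inputs (paired SD 7%, ICC 0.3) and falls to 0.775-0.812 under others (paired SD 10%, ICC 0.3). Those SDs and ICCs are assumptions. The figures bear on target (4) only if its margin of 0.05 means the 5% of 6.3, which the plan does not say. The point should be fixed, but it does not show that the study is too small.

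**What to change.** **Section 6.3.** State that the test is paired (recovered versus true in the same region) and that the patient is the independent unit. Restate power separately for 15 and 20 patients over a stated range of ICC, SD of recovered-minus-true percent differences, and mean number of lesion and normal tissue regions per patient. Take the SD and ICC from the Phase I data if they allow it; otherwise label them as assumptions. Do not claim 0.95 for the 15-subject arms without giving the region count and ICC it requires.

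**Section 6.2.3, target (4).** State whether the 0.05 margin is the 5% of 6.3 or an absolute SUV difference. Replace the reference to 95% power with a patient-clustered confidence interval for the mean recovered-minus-true difference (random patient intercept, patient means or patient-level bootstrap), and compare that interval with the margin.

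**Cost.** One rewritten paragraph and one specified analysis. The stated power may become less favourable. No extra patients or scans.

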One challenge of evaluating rapid multi-tracer PET techniques is the need to know the ground truth when evaluating results. For example, one possible study design would be to obtain separate, single-tracer scans with each tracer on separate days, and then to obtain simultaneous dual-tracer scans on a 3rd day—all in the same patient. Here the separate-scan images of each tracer could be used as the standard for evaluating images of each tracer recovered from the dual-tracer scans. However, such an approach would pose many problems, in particular: (1) high cost, scheduling challenges, and patient compliance issues for performing 3 different PET/CT exams on 3 different days; (2) increased radiation exposure from 3 PET/CT exams (3 CTs and 4 total PET tracer administrations); (3) test-retest variability for PET is on the order of 10-15% [99-101]—differences that can be larger than the errors in recovered dual-tracer images and thus limit the value of the study; and (4) it would only allow for a single dual-tracer scanning protocol to be studied (rather than allowing for various scanning protocols to be studied and compared).

A better and widely-accepted approach, used by our group and others [2-8, 10-13] is to acquire separate, single-tracer PET scans with each tracer and then retroactively combine the images to “synthesize” dual-tracer images which are ~identical to the images that would have been obtained from actual dual-tracer scanning. When more than one PET tracer is present during a scan, the resulting image represents the sum of all tracer present. As such, the images from separate, single-tracer PET scans can be added together to create “synthesized” multi-tracer PET images. Aside from small differences in scanner deadtime and random coincidence rates (which are well-understood and accurately corrected by the PET scanner), such synthesized dual-tracer images accurately mimic actual multi-tracer PET images, which characteristics that closely match what would have been obtained from actual multi-tracer scanning.

The advantage of this approach is that the actual single-tracer components of the resulting dual-tracer images are known exactly — and they can be used to evaluate the accuracy of individual-tracer images recovered from the multi-tracer images. In effect, the data become their own controls when using this approach.

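### The 0.95 power behind N = 104 in section 6.3 is for one pooled comparison in one tracer; the conclusion in 6.2.3 needs both tracers of a pair, for which the stated size gives about 0.90

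*Combined protocol and SAP*

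**What the plan says.** Section 6.3 sizes the study on differences in SUVmean "for lesions and normal tissue regions in images recovered from dual-tracer scanning for each tracer", with the hypothesis that these "are less than 5% different than those from the single-tracer" images. It does so "using a 2 sided *t*-test with alpha = 0.05 and desired power = 0.95" and takes an SD of 10% from PET test-retest variability. The result is N = 104 regions. Dividing by 5-7 regions or lesions per subject, the section says "this gives 15-20 subjects needed to obtain the desired statistical power", and it treats this as support for 15-20 patients in each arm.

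Section 6.2.3 lists four targets, joined by 'and', for concluding that the recovered images of each tracer are equivalent to single-tracer images. Target (4) asks for "tumor and background tissue SUVs for dual-tracer images within 0.05 of those for the separate-scan standard images" and attaches 95% power to it. The analyses are repeated for each tracer pair, so each arm reaches its own conclusion. Section 1.0 sets 15 subjects in each of Arms 1 and 2 and 20 in Arm 3.

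**The concern.** The sample-size section and the decision rule do not refer to the same event. Section 6.3 gives the power of one comparison in one tracer, using a count that mixes lesions with normal tissue. The conclusion in 6.2.3 requires success in two tracers, and target (4) names two tissue classes. A requirement that several comparisons all succeed has lower power than any one of them, unless they are perfectly correlated. If the tissue classes are judged apart, each also has only a share of the 104 values.

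If this is left as it stands, a missed target (4) in one tracer or tissue class could be read as an algorithm failing a test that had 95% power, when too few values might explain the result.

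**Working it through.** **Inputs.** From 6.3: margin 5%, SD 10%, two-sided alpha 0.05, power 0.95, 5-7 regions per subject. From 1.0: 15, 15 and 20 subjects. I read the 0.05 in target (4) as the 5% margin of 6.3, and treat regions as independent, as 6.3 does.

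**Step 1: reproduce the plan's figure.** For two means, n = 2 × (1.960 + 1.645)² × (10/5)² = 103.96, so 104. A two-sample equivalence test (two one-sided tests at 0.05, no true bias) also gives 104. So does a paired test if the SD of the difference is √2 × 10%. Conversion to subjects: 104/7 = 14.9 and 104/5 = 20.8. The figure stands as the size for one comparison.

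**Step 2: two tracers at 104 regions each.** If independent, 0.95² = 0.90. With correlation 0.5 it is 0.91, and with correlation 0.8 it is 0.92. The ceiling, under perfect correlation, is 0.95.

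**Step 3: planned arm sizes, tissues pooled.** Power for one tracer is Φ(5 / (10 × √(2/n)) − 1.960). For both tracers, taken as independent, it is the square of this.

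| Arm | Regions | One tracer | Both tracers |
|---|---|---|---|
| 1 and 2 | 15 × 5 = 75 | 0.86 | 0.75 |
| 1 and 2 | 15 × 7 = 105 | 0.95 | 0.91 |
| 3 | 20 × 5 = 100 | 0.94 | 0.89 |
| 3 | 20 × 7 = 140 | 0.99 | 0.97 |

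**Step 4: tumor and background judged separately from the same regions.** However the regions divide, the smaller class has at most half of them: 105/2, so 52, in Arms 1-2, and 140/2 = 70 in Arm 3.

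- Difference test, n = 52: Φ(2.550 − 1.960) = 0.72. For n = 70: Φ(2.958 − 1.960) = 0.84.
- Equivalence test with no true bias, n = 52: 2 × Φ(2.550 − 1.645) − 1 = 0.63. For n = 70: 2 × Φ(2.958 − 1.645) − 1 = 0.81.

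The joint power of an arm cannot exceed that of its weakest comparison. On this reading 95% is therefore not reached in any arm, whatever the correlation and whatever the split.

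**The case against.** Four points on the other side carry weight.

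*No arm-level power is claimed.* Section 6.3 attaches 0.95 to each tracer, and its mention of each arm concerns the number of patients. A reader might infer that the plan promises 0.95 for an arm's whole conclusion. It does not say so. What stands is that the per-tracer figure is used to justify each arm's size and that no joint figure is given.

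*Separate testing by tissue is not explicit.* A reader might infer four mandatory tests per arm (two tracers, two tissues) and multiply four powers for an evenly divided 104. The documents do not support that as the plan's rule. Target (4) names both tissues without saying that they are tested apart, section 6.2.2 describes regression over lesion and background regions without separating them, and no even split is stated. Such a product would also use the power of a difference test for what is an equivalence target. If the tissues are pooled, Arm 3 at 7 regions per subject reaches 0.97 for both tracers. If 5-7 regions were meant for each class, Arm 3 at 7 per class would have 140 values per comparison and about 0.95 over four independent comparisons (0.987⁴), and Arms 1-2 at best about 0.82 (0.952⁴).

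*The 10% SD may be too large.* A reader might infer from the 10-15% test-retest range in section 6.1 that 10% is optimistic. That range is given there as a drawback of a rejected three-scan design. In the chosen design the recovered and true values come from the same acquisition, and 6.1 notes that rescan differences can be larger than recovery errors. If the SD of the paired difference were 10%, 52 regions would already give 0.95 for one comparison. At 8% (an assumption), four such comparisons would have 0.98 jointly. This stands as a reason why actual power may exceed 0.95, but 6.3 neither uses nor justifies a paired SD.

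*The consequence is limited.* The primary objective is to obtain data for algorithm development, and nothing says that a missed target (4) ends that work. This limits the stakes. It does not make the power statement match the conclusion.

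**Conclusion.** The point holds in a limited form. N = 104 is correct for one comparison in one tracer, pooled over lesions and normal tissue, and 0.95 should not be carried over to the conclusion in 6.2.3. Arms 1-2 fall short of 0.95 for both tracers across the whole 5-7 range if the tracers are independent. Arm 3 falls short at 5 regions per subject but not at 7 when tissues are pooled. If target (4) is judged by tissue class from the same regions, the shortfall extends to every arm.

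These figures rest on 6.3's formula, its 10% SD and independent regions. The two-tracer figures also assume independence between tracers, and positive correlation would raise them somewhat. Targets (1) to (3) have no power calculation; requiring them as well can only lower the joint power. The size of the gap thus depends on matters the plan leaves open: pooled or separate judgment, regions per class, and the SD of the paired difference.

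**What to change.** In section 6.3:

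- Say that 0.95 refers to one comparison in one tracer, pooled over regions.
- State whether target (4) is judged pooled or separately for tumor and background.
- Give the expected number of regions in each class for 15 and for 20 subjects.
- Restate the joint power for each arm's conclusion, using one test throughout: the equivalence test that matches target (4).
- Say that actual power may be higher if the SD of the paired recovered-minus-true difference is below the value assumed.

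No patients are added. No alpha adjustment is needed, because all comparisons must pass. The cost is a rewording of 6.3 and a stated power that looks less favourable.
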